4.1.2. Day 1 of Crossover for Crossover Participants

For participants who cross over from TG10/TG20 to TG5D, Day 1 of crossover is the date that the participants are assigned to TG5D based on the assigned dose in the exposure CRF.

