### **5.2.3. Crossover of Part 2 or Part 3 Subjects**

It is anticipated that approximately 15 to 20 subjects will have been enrolled into Part 2. With IRB approval of Protocol Amendment 5 at a given site, subjects randomized to TG10 at that site may cross over to either 20 mg QD followed by 5 mg QD after Week 8 (if subject is within the first 8 weeks of treatment at the time of crossover), or to 5 mg QD (if subject is beyond 8 weeks of treatment and receiving 10 mg once weekly at the time of crossover). With IRB approval of Protocol Amendment 6 at a given site, subjects randomized to TG20 at that site may cross over to 5 mg QD once Week 8 has been reached. All potential crossover subjects must meet all of the following criteria:

1. Spleen size by palpation at most recent visit has decreased by < 25% from baseline while on study.
2. Has recent history of adequate bone marrow reserve as demonstrated by the following:
  - a. Platelet count  $\geq 50 \times 10^9/L$  in the 4 weeks before crossover.
  - b. ANC levels  $\geq 0.5 \times 10^9/L$  in the 4 weeks before crossover.
3. Has adequate liver function at most recent study visit as demonstrated by the following:
  - a. Direct bilirubin  $< 2.0 \times$  the ULN. (NOTE: direct bilirubin will only be determined if total bilirubin is  $\geq 2.0 \times$  ULN).
  - b. ALT or AST  $< 2.5 \times$  ULN.
4. Has adequate renal function at most recent visit as demonstrated by creatinine clearance  $> 50 \text{ mL/min}$  measured or calculated by Cockcroft-Gault equation.
5. Subject has been at least 85% compliant with study drug administration per drug accountability assessments at visits to date.
6. Subject has not developed a cardiovascular or gastrointestinal condition since Day 1 that would have excluded him/her from study entry.

Subjects who do not meet these criteria, or subjects who do meet the criteria but do not wish to cross over, may continue on the originally assigned regimen, and may crossover at any time provided the criteria for crossover are met and crossover is determined by subject and investigator to represent the best option.

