3.5. Crossover Portion

With IRB approval of Protocol Amendment 5 at a given site, participants randomized to TG10 in Part 2 at that site may cross over to either 20 mg QD followed by 5 mg QD after Week 8 (if participant is within the first 8 weeks of treatment at the time of crossover), or to 5 mg QD (if participant is beyond 8 weeks of treatment and receiving 10 mg once weekly at the time of crossover). With IRB approval of Protocol Amendment 6 at a given site, participants randomized to TG20 at that site may cross over to 5 mg QD once Week 8 has been reached. All potential crossover participants must meet the criteria listed in Protocol Amendment 6, Section 5.2.3.

Participants who do not meet these criteria, or participants who do meet the criteria but do not wish to cross over, may continue on the originally assigned regimen, and may crossover at any time provided the criteria for crossover are met and crossover is determined by participant and investigator to represent the best option.

The crossover portion starts when the participants are assigned to and receive their first dose of a different treatment. The original portion of the study for crossover participants ends the day before crossover.

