5.2. Treatment Groups

As the study was terminated early, participants from all parts will be combined. Data will be summarized overall and by treatment group based on the dose regimen initially assigned in the initial portion:

- TG10: Ruxolitinib at stable dose plus INCB050465 10 mg QD for 8 weeks followed by 10 mg once weekly.
- TG20: Ruxolitinib at stable dose plus INCB050465 20 mg QD for 8 weeks followed by 20 mg once weekly.
- TG5, TG5I/M: Ruxolitinib at stable dose plus INCB050465 20 mg QD for 8 weeks followed by 5 mg QD.
- TG5D: Ruxolitinib at stable dose plus INCB050465 5 mg QD from Day 1 until EOT visit.

Note that TG5I/M in Part 4 is identical to TG5 from Part 3; participants from these 2 groups will be combined in the final analysis.

The crossover participants will be summarized in the initial portion from the date of randomization to the date before crossover.

In the crossover portion, the crossover participants will be summarized in TG5D from the date of crossover to the end of study. Only the crossover participants will be summarized in the crossover portion. Participants in TG5 (TG5I/M) and TG5D and the participants in TG10 or TG20 who do not meet the crossover criteria will remain in the treatment group initially assigned in the initial portion.

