5.3. Analysis Populations

5.3.1. Safety Population

The safety population includes all participants in Parts 1, 2, 3, and 4 who received at least 1 dose of study drug. Treatment groups for this population will be determined according to the actual treatment the participant received regardless of assigned study drug treatment. The safety population will be used for all analyses.

The participants in TG5D and TG5 (TG5I/M) will be summarized under TG5D and TG5 (TG5I/M), respectively, in the initial portion. The participants crossed over from TG10/TG20 to TG5D will be summarized under TG10/TG20 in the initial portion before crossover and under a separate crossover group after crossover.

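### The SAP gives crossover two start dates and two labels, so 20 mg daily time in early TG10 crossovers can be reported under TG10 or under TG5D, and neither describes it

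*SAP*

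**What the plan says.** **Routes.** Under SAP Section 3.5, TG10 participants still in their first 8 weeks "may cross over to either 20 mg QD followed by 5 mg QD after Week 8"; those beyond Week 8 go straight to 5 mg daily. TG20 participants may go to 5 mg daily once they reach Week 8. Protocol Section 5.2.3 gives the same routes: "subjects randomized to TG10 at that site may cross over to either 20 mg QD followed by 5 mg QD after Week 8".

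**Start date.** Section 3.5 says: "The crossover portion starts when the participants are assigned to and receive their first dose of a different treatment". It adds: "The original portion of the study for crossover participants ends the day before crossover". Section 4.1.2 says: "For participants who cross over from TG10/TG20 to TG5D, Day 1 of crossover is the date that the participants are assigned to TG5D", with the date read from the assigned dose on the exposure CRF.

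**Label.** Section 5.2 says that, in the crossover portion, "the crossover participants will be summarized in TG5D from the date of crossover to the end of study". Section 5.3.1 puts the same people "under a separate crossover group after crossover". Section 5.3.3 defines the crossover population solely by a move from TG10 or TG20 to TG5D. In Section 5.2's own list, TG5D is 5 mg daily from Day 1 with no 20 mg period; 8 weeks of 20 mg daily followed by 5 mg daily is TG5 or TG5I/M.

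**The concern.** For a TG10 participant who moves first to 20 mg daily, the first dose of a different treatment and the assignment to 5 mg daily are different days. The crossover date decides which table an event enters, because exposure (Section 6.4), adverse events of special interest (Section 8.2.4) and the adverse event, laboratory and symptom tables in Appendix A are split into initial and crossover portions. Two programmers could each follow the SAP and produce different TG10 tables.

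One would report weeks at twice the assigned daily dose under TG10. The other would report them in a portion headed TG5D, a regimen that contains no 20 mg dosing. Either result blurs a dose-by-dose safety description. The label has a wider but milder problem: every crossover participant took 10 mg or 20 mg before reaching 5 mg, so a definition that starts at 5 mg on Day 1 does not describe their history.

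**Working it through.** The plan gives no figure on this point, so there is none to reproduce. The check compares the rules and then counts days.

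**1. Where the dates differ**

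| Route | Start under 3.5 | Start under 4.1.2 |
|---|---|---|
| TG20 to 5 mg daily | first 5 mg dose | assignment to 5 mg: essentially the same date |
| TG10 beyond Week 8 to 5 mg daily | first 5 mg dose | assignment to 5 mg: essentially the same date |
| TG10 within 8 weeks to 20 mg, then 5 mg daily | first 20 mg dose | assignment to 5 mg: later |

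Only the third route is affected by the date conflict.

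**2. Day count, with Week 8 counted from study Day 1 (assumption A)**

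Let c be the study day of the first 20 mg dose, an assumed value. The 5 mg dose then starts on Day 57. Days at 10 mg = c − 1; days at 20 mg = 57 − c; together 56. Under 4.1.2 the TG10 initial portion is Days 1 to 56, and its average daily dose is [10(c − 1) + 20(57 − c)] / 56.

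| c | Days at 20 mg in TG10 under 4.1.2 | Share of 56 days | Average daily dose, mg | Days at 20 mg in TG10 under 3.5 |
|---|---|---|---|---|
| 8 | 49 | 87.5% | 18.8 | 0 |
| 29 | 28 | 50.0% | 15.0 | 0 |
| 43 | 14 | 25.0% | 12.5 | 0 |
| 56 | 1 | 1.8% | 10.2 | 0 |

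Under 3.5 the initial portion ends on Day c − 1, and the same 57 − c days fall in the crossover portion.

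**3. Day count, with 8 weeks at 20 mg counted from crossover (assumption B)**

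Days at 20 mg = 56, and 5 mg starts on Day c + 56. Under 4.1.2 the share of the TG10 initial portion at 20 mg is 56 / (c − 1 + 56): 56/63 = 88.9% for c = 8, 56/84 = 66.7% for c = 29, and 56/111 = 50.5% for c = 56. Under 3.5 it is again 0.

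**4. Spleen scans**

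The first scheduled post-baseline scan is Week 12, Day 84 ± 7 in SAP Section 7.3.1. Under A, crossover has begun by Day 57 on either rule, so no scheduled post-baseline scan falls in the 20 mg period. Under B, a Day 84 scan precedes the 5 mg dose when c + 56 > 84, that is c ≥ 29. Rule 4.1.2 would then place that scan in the TG10 initial portion, which feeds the added daily versus daily/weekly comparison.

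**5. Reach**

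Protocol Section 4.3.1 reports 20 participants in Part 2, randomized 1:1, so about 10 in TG10. SAP Section 5.2 pools all parts. Part 1 enrolled 10. With Cohort 2 planned at 6 and Cohort 1 at 3, Cohort 1 is inferred at 3 to 4, which makes pooled TG10 about 13 to 14. One early crossover is then 1/14 = 7.1% to 1/13 = 7.7% of the group.

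**The case against.** The strongest reply is that Section 3.5 already gives a workable rule. Section 4.1.2 speaks only of crossover to TG5D, and a TG10 participant starting 20 mg is not making that crossover at that moment, so 3.5 can govern and no 20 mg day need enter TG10. This defeats the inference a reader might draw that 20 mg time will certainly be credited to the 10 mg group; the documents support that outcome under one of two rules. It does not remove the conflict. Section 4.1.2 is the section that defines crossover Day 1, Section 5.3.3 recognizes no crossover other than to TG5D, and nothing says which section prevails.

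Section 5.3.1 also groups by actual treatment received. That does not settle the matter, because its next paragraph divides time into before and after crossover, which is the date in dispute.

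On labels, Section 5.2 restricts the crossover portion to crossover participants, and Appendix A has separate crossover tables. A reader might infer that crossovers are pooled with participants randomized to TG5D; the documents do not support that. For direct crossovers to 5 mg daily, TG5D does match the dose from crossover onward, though not the earlier exposure.

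Reach is also narrow. The 20 mg route required a TG10 participant still within 8 weeks when the site approved Amendment 5, which also closed Part 2 enrollment there. It further required a palpable spleen decrease below 25%, at least 85% compliance, and adequate marrow, liver and renal function. About 28 participants had already been treated in Parts 1 and 2 by March 2018, against 10 + 20 = 30 in all. The documents do not show that anyone took this route. All of this limits the size of the problem and stands.

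**Conclusion.** The point holds as an internal contradiction in the SAP. For TG10 participants who cross within 8 weeks to 20 mg then 5 mg daily, the 20 mg period falls in TG10 under Section 4.1.2 and in the crossover portion under Section 3.5; that portion is then labelled TG5D by Section 5.2 and a separate group by Section 5.3.1. Neither TG10 nor TG5D describes the sequence.

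Under assumption A the disputed time runs from 1 to 49 days per participant for c from 56 down to 8. The switch days are illustrative, since the documents give neither dates nor the number crossing. The date conflict is bounded by about 10 Part 2 participants and bears on TG10 exposure, adverse event, laboratory and early symptom summaries. The label conflict covers all crossover participants, within separate tables.

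Two larger readings are not supported. A reader might infer that the main efficacy comparison is contaminated; TG5D versus TG5 (TG5I/M) uses the initial portion, so crossovers do not enter it. A reader might also infer that spleen scans on 20 mg would be reported under 10 mg; for scheduled scans this needs assumption B as well as rule 4.1.2. The matter should be corrected because the remedy is cheap and the TG10 safety tables otherwise depend on which section is followed.

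**What to change.** Reconcile SAP Sections 3.5, 4.1.2, 5.2, 5.3.1 and 5.3.3:

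- Define crossover Day 1 once, as the date of the first dose of a regimen different from the one assigned, following Section 3.5, and have 4.1.2 refer to it.
- Use one destination after crossover, the separate crossover group of Section 5.3.1, and remove the TG5D label for crossover time from 4.1.2, 5.2 and 5.3.3.
- Within that group, identify the route through 20 mg daily then 5 mg daily separately from direct crossover to 5 mg daily. If very few took the first route, a listing would serve.
- State how many participants took each route.

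The cost is SAP wording and table labels. No new data and no change to the efficacy tests are needed.

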4.1.3. Study Day

If a visit/reporting date is on or after Day 1, then the study day at the visit/reporting date will be calculated as

Day # = (Visit/Reporting Date – Day 1 date + 1).

If the visit/reporting date is before Day 1, then the study day at the visit/reporting date will be calculated as

Day # = (Visit/Reporting Date – Day 1 date).

A study day of -1 indicates 1 day before Day 1.

4.1.4. Baseline Value

Baseline is the last nonmissing measurement obtained within the baseline window before the first administration of INCB050465, unless otherwise defined.

For randomized participants not treated with any study drug, baseline is defined as the last nonmissing assessment before randomization for all parameters.

When scheduled assessments and unscheduled assessments occur on the same day and time of the assessment or time of first dose is not available, use the following convention to determine baseline:

- If both a scheduled and an unscheduled visit are available on the day of the first dose and the time is missing, use the scheduled assessment as baseline.
- If all scheduled assessments are missing on the day of the first dose and an unscheduled assessment is available, use the unscheduled assessment as baseline.

4.1.5. Last Available Value

The last available value is the last nonmissing measurement obtained after starting INCB050465 and within 30 days after the last dose of INCB050465.

4.1.6. Handling of Missing and Incomplete Data

In general, values for missing data will not be imputed unless methods for handling missing data are specified in this section or relevant sections.

Partial MF diagnosis date will be handled as follows:

- If only the day is missing, then the imputed day will be the first of the month.
- If both the month and day are missing, then the imputed day and month will be 01 JAN.
- No imputation will be done if the date is completely missing.

Missing or partial date of last dose will be handled as follows:

- If only the day is missing, then the imputed date of the last dose will be the earlier date of the first day of the month or the date that the participant discontinued treatment.
- Otherwise, the date that the participant discontinued treatment will be used as the date of the last dose.

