6.4. Exposure

For participants in the safety population, exposure to INCB050465 and ruxolitinib will be summarized descriptively by treatment group for initial portion and crossover portion separately as the following:

- **Duration of treatment with study drug (INCB050465):** Date of last dose of INCB050465– date of first dose of INCB050465 + 1
- **Duration of treatment with study drug (ruxolitinib):** Date of last dose of ruxolitinib – date of first dose of ruxolitinib + 1
- **Dose intensity for INCB050465:** Let S be the earliest study day after permanent discontinuation from study, last study visit, or participant death; let D_1, D_2, \dots, D_K , be the K daily doses (mg) of INCB050465 prescribed to the participant accounting for dose increases on study days S_1, S_2, \dots, S_K . Dose intensity for INCB050465 is defined as

$$\text{dose intensity (\%)} = 100 \times [\text{total dose (mg)}] / [\text{assigned dose (mg)}],$$

where a participant's assigned dose of INCB050465 is defined as the sum of the doses prescribed had the participant not experienced dose delays or reductions on each of the S study days. Formally expressed,

$$\text{assigned dose} = \sum_{i=1}^K D_i(t_{i+1} - t_i) \text{ where } t_1 = 1 \text{ and } t_{K+1} = S$$

For example, suppose a participant is assigned INCB050465 10 mg QD, dose escalates per investigator decision to 20 mg QD on Day 19, and discontinues on Day 31. The assigned dose of INCB050465 for the participant in question is

$$\text{assigned dose} = (19 - 1) \times 10 + (31 - 19) \times 20 = 420 \text{ mg.}$$

- **Dose intensity for ruxolitinib:** Let S be the earliest study day after permanent discontinuation from study, last study visit, or participant death; let D_1, D_2, \dots, D_K , be the K daily doses (mg) of ruxolitinib prescribed to the participant accounting for dose increases on study days S_1, S_2, \dots, S_K . Dose intensity for ruxolitinib is defined as

$$\text{dose intensity (\%)} = 100 \times [\text{total dose(mg)}]/[\text{assigned dose (mg)}],$$

where a participant's assigned dose of ruxolitinib is defined as the sum of the doses prescribed had the participant not experienced dose delays or reductions on each of the S study days. Formally expressed,

$$\text{assigned dose} = \sum_{i=1}^K D_i(t_{i+1} - t_i) \text{ where } t_1 = 1 \text{ and } t_{K+1} = S$$

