For example, suppose a participant is assigned ruxolitinib 10 mg BID, dose de-escalates per investigator decision to 5 mg BID on Day 19, and discontinues on Day 31. The assigned dose of ruxolitinib for the participant in question is

$$\text{assigned dose} = (19 - 1) \times 20 + (31 - 19) \times 10 = 480 \text{ mg.}$$

- **Average daily dose of INCB050465 (mg/day):** total actual INCB050465 dose taken (mg) / duration of treatment with INCB050465 (days).
- **Average daily dose of ruxolitinib (mg/day):** total actual ruxolitinib dose taken (mg) / duration of treatment with ruxolitinib (days).

Total actual dose taken will be calculated based on the information entered on the drug accountability CRF.

- **INCB050465 dose modifications:** Number of participants who had INCB050465 dose reduction, escalation, and interruption will be summarized.
- **Ruxolitinib dose modifications:** Number of participants who had ruxolitinib dose reduction, escalation, and interruption will be summarized.
- **Starting dose of ruxolitinib:** The starting dose of ruxolitinib at the time of the first dose of INCB050465 will be summarized.

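### SAP 4.1.6 sets a last-dose date with a missing day to the 1st of the month or earlier, with no floor at the first dose, so treatment duration can be zero or negative and average daily dose inflated

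*SAP*

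**What the plan says.** SAP section 4.1.6 has two rules for an incomplete date of last dose. The first applies when just the day is unknown: "the imputed date of the last dose will be the earlier date of the first day of the month"; the other date in that comparison is the day of treatment discontinuation. For anything less complete, the rule is: "Otherwise, the date that the participant discontinued treatment will be used as the date of the last dose". Neither rule names a drug, and neither sets a lower limit at the first dose.

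SAP section 6.4 defines the duration of INCB050465 treatment as "Date of last dose of INCB050465– date of first dose of INCB050465 + 1", again with no lower limit. Average daily dose is the total actual dose divided by that duration. For the numerator: "Total actual dose taken will be calculated based on the information entered on the drug accountability CRF". The total is therefore not cut off at the imputed last-dose date. Ruxolitinib duration and average daily dose are defined in the same way.

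**The concern.** The day-missing rule is a minimum of two dates, and one of them is the 1st of the month. The discontinuation date can only move the result earlier. Two consequences follow.

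- If the first dose was given after the 1st of that same month, the imputed last dose precedes the first dose, or falls so that duration is zero.
- If the last dose was in a later month, the imputed treatment period is too short, but the tablets counted still cover the whole period. Numerator and denominator of the average daily dose then refer to different spans of time.

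At stake is the credibility of the exposure tables. A negative duration is impossible, and an average above every prescribed dose would read as overdosing. One such record can visibly distort a minimum, maximum or mean in a small treatment group.

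**Working it through.** **Inputs.** Imputation rule: SAP 4.1.6. Duration and average daily dose: SAP 6.4. Dose levels of 20 mg and 5 mg once daily: SAP 5.2. Expected participation of about 24 months: Protocol 4.4. The calendar dates below are assumed for illustration, with full compliance unless stated.

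**Check that SAP 6.4 is read correctly.** Its worked assigned dose is (19 - 1) × 10 + (31 - 19) × 20 = 180 + 240 = 420 mg, which matches the SAP.

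**Case 1: first and last dose in the same month.** With the first dose on day d, the imputed duration is at most (1 - d) + 1 = 2 - d days.
- d = 1: 1 day. At 20 mg once daily from 1 to 28 MAR, 560 mg / 1 day = 560 mg/day.
- d = 2: 0 days, so average dose is undefined.
- d = 3 or later: negative. For a first dose on 10 MAR and a last dose in MAR with day unknown, 2 - 10 = -8 days. If the true last dose was 28 MAR at 20 mg once daily, the true duration is 19 days and the total 380 mg, and the average becomes 380 / (-8) = -47.5 mg/day.

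**Case 2: last dose in a later month.** The shortfall is (true day of month - 1), so at most 31 - 1 = 30 days.
- 20 mg once daily, 20 JAN to 25 FEB, last day unknown. True duration: 37 days, 37 × 20 = 740 mg, 20 mg/day. Imputed: 20 JAN to 1 FEB = 13 days, and 740 / 13 = 56.9 mg/day.
- 5 mg once daily, 15 MAR to 31 MAY. True: 78 days, 390 mg. Imputed: 48 days, and 390 / 48 = 8.1 mg/day.
- 5 mg once daily for 383 days ending on the 31st: 1915 mg / 353 days = 5.42 mg/day.
- The SAP's 420 mg over 30 days (true average 14.0 mg/day): started on 15 MAR, 420 / 18 = 23.3 mg/day, above the highest prescribed dose of 20 mg; started on 10 MAR, 420 / 23 = 18.3 mg/day, below it.

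**Average size.** With the true day of month uniform (assumed), the mean shortfall is about 15 days. Against 8 weeks, 15 / 56 = 27%. Against 24 months (about 730 days), 15 / 730 = 2%.

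**The 30-day window.** SAP 4.1.5 takes values "within 30 days after the last dose of INCB050465". For a last dose in March, 1 MAR + 30 days = 31 MAR; in February, 1 FEB + 30 days = 3 MAR. Every value taken up to the true last dose stays inside. A post-dose value can fall outside: with a true last dose on 31 MAR and a test on 5 APR, the test is 5 days after the true date but 35 days after the imputed one.

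**The case against.** The strongest reply is that the reach is small. The date of last dose is a required CRF item (Protocol 5.6.2), an end-of-treatment visit is held at discontinuation (Protocol 6.4) and tablets are counted at visits (Protocol 5.4), so dates with a missing day should be uncommon. Duration and average daily dose are descriptive. Dose intensity (SAP 6.4) runs to a study day set by study discontinuation, last visit or death; compliance (SAP 6.5) uses the prescribed dose. As written, neither depends on the imputed date, and nor does the primary spleen-volume comparison. A first-of-month convention is also a recognisable choice that errs towards understating exposure, as a month-end convention errs the other way. All of this stands as a limit on importance. It does not rescue a rule that returns negative durations.

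Three stronger readings are tempting, and the documents do not support them.

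- **That on-treatment laboratory values are dropped.** The window arithmetic shows that they are not. The exception would need a discontinuation date in a month before the recorded last-dose month, which is a data conflict. Only post-dose values inside the intended window could be lost, and only if that window is keyed to the imputed date. The laboratory shift-table rule in SAP 8.3.2 counts from stopping study treatment and does not mention the imputed date.
- **That knowing the month always gives a worse estimate than knowing nothing**, because a wholly missing date takes the discontinuation date. Discontinuation can trail the last dose, since Protocol 5.5.6 and 5.5.7 foresee delays of up to 14 days, or longer after sponsor involvement. With a last dose on 3 MAR and discontinuation on 20 MAR (assumed), the month rule is 2 days off and the discontinuation date 17.
- **That a 27% understatement is typical.** Eight weeks is the length of the initial daily phase in most regimens. Treatment itself is open-ended.

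**Conclusion.** The rule is wrong as written, and the point is minor. For a participant with a day-missing last-dose date, it gives a duration of zero or less whenever dosing began after the 1st and ended in the same month. When the last dose is in a later month, duration is up to 30 days too short, and average daily dose is inflated relative to the accountability total. The inflated figure can exceed every prescribed dose, but need not do so if compliance was low or the dose varied, and the distortion fades with long treatment. The mean shortfall of about 15 days rests on a uniform day of month and ranges from about 27% of an 8-week exposure to about 2% of 24 months. The documents do not say how many participants have partial dates; the number is likely low. Only their descriptive exposure summaries are affected, apart from the possible loss of some post-dose values noted above.

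**What to change.** Replace the day-missing rule in SAP 4.1.6 with: the earlier of the last day of the recorded month and the treatment discontinuation date, and never before the first dose or the last visit with recorded dosing.

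Applied to the 20 JAN to 25 FEB example (non-leap year), this gives 37 to 40 days, depending on the discontinuation date, and 740 / 40 = 18.5 to 740 / 37 = 20 mg/day. For 10 to 28 MAR it gives 19 to 22 days.

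A floor at the first dose is the minimum change, but is not enough alone. It removes the negative values, yet the February example stays at 13 days and 56.9 mg/day, and the March example becomes 1 day and 380 mg/day.

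The cost is one SAP sentence and the matching derivation. The downside is a slight overstatement of exposure, and so a slight understatement of average daily dose, in the few affected participants.
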